16264901000119100'		Recurrent moderate major depressive disorder co-occurrent with anxiety (disorder)
16265301000119100'		Recurrent major depressive disorder in partial remission co-occurrent with anxiety (disorder)
16265951000119100'		Mild major depressive disorder co-occurrent with anxiety single episode (disorder)
16266831000119100'		Moderate major depressive disorder co-occurrent with anxiety single episode (disorder)
16266991000119100'		Severe major depressive disorder co-occurrent with anxiety single episode (disorder)
Anxiety episode		
Read V2 Code	Term ID	Description
E200.	All	Anxiety states
E2000	All	Anxiety state unspecified
E2001	All	Panic disorder
E2002	All	Generalised anxiety disorder
E2003	All	Anxiety with depression
E2004	All	Chronic anxiety
E2005	All	Recurrent anxiety
E200z	All	Anxiety state NOS
Eu41.	All	[X]Other anxiety disorders
Eu410	All	[X]Panic disorder [episodic paroxysmal anxiety]

Eu411	All	[X]Generalized anxiety disorder
Eu412	All	[X]Mixed anxiety and depressive disorder
Eu413	All	[X]Other mixed anxiety disorders
Eu41y	All	[X]Other specified anxiety disorders
Eu41z	All	[X]Anxiety disorder, unspecified
Read CTV3 Code	Term ID	Description
E200.	All	Anxiety disorder
XE1Y7	All	Panic disorder
Eu410	All	[X]Panic disorder [episodic paroxysmal anxiety]
E2002	All	Generalised anxiety disorder
X00Sb	All	Mixed anxiety and depressive disorder
X00RP	All	Organic anxiety disorder
E2004	All	Chronic anxiety
E2005	All	Recurrent anxiety
E200z	All	Anxiety state NOS
X00Sc	All	Anxiety hysteria
Eu41.	All	[X]Other anxiety disorders
Eu413	All	[X]Other mixed anxiety disorders
Eu41z	All	[X]Anxiety disorder, unspecified
XE1Zj	All	[X]Other specified anxiety disorders
SNOMED Code	Term ID	Description
1037451000000100'		Referral for psychological management of anxiety (procedure)
1053831000000100'		Signposting to Anxiety UK (procedure)
10586006'		Occupation-related stress disorder (disorder)
10743001000119100'		Anxiety disorder in mother complicating childbirth (disorder)
109006'		Anxiety disorder of childhood OR adolescence (disorder)

111487009'		Dream anxiety disorder (disorder)
11458009'		Anticipatory anxiety, mild (finding)
11806006'		Separation anxiety disorder of childhood (disorder)
12398201000119100'		Anxiety disorder caused by methamphetamine (disorder)
126943008'		Separation anxiety (disorder)
13438001'		Overanxious disorder of childhood (disorder)
15277004'		Hallucinogen-induced anxiety disorder (disorder)
161470009'		History of anxiety state (situation)
16264621000119100'		Recurrent mild major depressive disorder co-occurrent with anxiety (disorder)
16264821000119100'		Recurrent severe major depressive disorder co-occurrent with anxiety (disorder)
16264901000119100'		Recurrent moderate major depressive disorder co-occurrent with anxiety (disorder)
16265301000119100'		Recurrent major depressive disorder in partial remission co-occurrent with anxiety (disorder)
16265701000119100'		Illness anxiety disorder (disorder)
16265951000119100'		Mild major depressive disorder co-occurrent with anxiety single episode (disorder)
16266831000119100'		Moderate major depressive disorder co-occurrent with anxiety single episode (disorder)
16266991000119100'		Severe major depressive disorder co-occurrent with anxiety single episode (disorder)
162723006'		On examination - anxious (finding)
1686006'		Sedative, hypnotic AND/OR anxiolytic-induced anxiety disorder (disorder)
17496003'		Organic anxiety disorder (disorder)
191708009'		Chronic anxiety (finding)
191709001'		Recurrent anxiety (finding)
192108001'		Disturbance of anxiety and fearfulness in childhood and adolescence (disorder)

192611004'		Childhood phobic anxiety disorder (disorder)
197480006'		Anxiety disorder (disorder)
198288003'		Anxiety state (finding)
207363009'		Anxiety neurosis (finding)
21897009'		Generalized anxiety disorder (disorder)
225216003'		Acknowledging anxiety (procedure)
225624000'		Panic attack (finding)
22621000119103'		Anxiety disorder caused by drug (disorder)
228560001'		Anxiety management training (procedure)
231502005'		Situational panic attack (finding)
231503000'		Non-situational panic attack (finding)
231504006'		Mixed anxiety and depressive disorder (disorder)
231506008'		Anxiety hysteria (finding)
247805009'		Anxiety and fear (finding)
286644009'		Level of anxiety (finding)
286710008'		Anxious character (finding)
286711007'		Over-anxious character (finding)
286712000'		Fearful character (finding)
300895004'		Anxiety attack (finding)
313087008'		Counseling for anxiety (procedure)
34938008'		Alcohol-induced anxiety disorder (disorder)
351861000000106'		Stranger anxiety (disorder)
35429005'		Anticipatory anxiety (finding)
35607004'		Panic disorder with agoraphobia (disorder)
36646009'		Anticipatory anxiety, moderate (finding)
371631005'		Panic disorder (disorder)

37868008'		Anxiety disorder of adolescence (disorder)
37872007'		Avoidant disorder of childhood OR adolescence (disorder)

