The Optimum Patient Care Research Database (OPCRD). This database incorporates pseudonymised primary care records from 700 GP practices distributed across England, Wales, Scotland and Northern Ireland. The current OPCRD cohort size is over 5 million actively registered people, and historic records available for 10.1 million people. The cohort dataset can be enhanced through direct-to-patient and direct-to-care provider questionnaires at additional cost if required.

Study design

The proposed study will use the retrospectively collected data of all eligible patients within the database at the date of data extraction. Within this primary care cohort, all patients with IBD comprising of the three main subtypes; ulcerative colitis (UC), Crohn's disease (CD) and IBD unclassified (IBDU), excluding microscopic colitis, radiation induced enterocolitis and drug-induced enterocolitis, will be identified using diagnostic codes and prescription records. A diagnostic algorithm will be developed to facilitate robust case identification of IBD and IBD subtypes, as well as mental health outcomes.

Statistical methods

We will use standard descriptive statistics (mean, standard deviations, etc) to describe the characteristics of the study cohort.

Recorded sociodemographic characteristics and clinical features

Sociodemographic data will comprise by age group, age at diagnosis, gender, ethnicity, and socioeconomic status. Ethnicity will be categorised as follows to be consistent with the UK official census categories: White, Asian, Black African/Caribbean, Mixed, and Other. The index of multiple deprivation (IMD) will be used as a measure of socioeconomic status. This is derived from patient postcode at the point of data extraction.

Stream 1: Study Cohort

Stream 1: Definition of people with new onset IBD

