X303e	All	Proctocolitis
J41y.	All	Other idiopathic proctocolitis

J41yz	All	Other idiopathic proctocolitis NOS
J41z.	All	Idiopathic proctocolitis NOS
X304F	All	Caecitis
SNOMED Code	Term ID	Description
24526004		Inflammatory bowel disease (disorder)
721686000		Inflammatory polyps co-occurrent and due to inflammatory bowel disease (disorder)
6382002		Chronic inflammatory small bowel disease (disorder)
771333006		Immune dysregulation, inflammatory bowel disease, arthritis, recurrent infection syndrome (disorder)
128999004		Inflammatory disorder of digestive tract (disorder)
64226004		Colitis
54597004		Chronic colitis (disorder)
369445005		Chronic proctocolitis (disorder)
369447002		Chronic proctocolitis, confluent (disorder)
369446006		Chronic proctocolitis, patchy (disorder)
52506002		Chronic ulcerative rectosigmoiditis (disorder)
373639002		Distal colitis (disorder)
51290000		Diversion colitis (disorder)
29120000		Eosinophilic colitis (disorder)
783185002		Focal active colitis (disorder)
359660000		Idiopathic colitis (disorder)
235746007		Indeterminate colitis (disorder)
43752006		Inflammation of small intestine and colon (disorder)
13470001		Chronic ulcerative ileocolitis (disorder)
71207007		Noninfectious enteritis (disorder)
735731005		Chronic non-infectious enteritis of uncertain etiology (disorder)
307418008		Non-infective enteritis and colitis (disorder)
14066009		Noninfectious colitis (disorder)

414155001		Exacerbation of non-infective colitis (disorder)
53372009		Noninfectious sigmoiditis (disorder)
788718000		Iritis co-occurrent with inflammatory bowel disease (disorder)
64613007		Inflammation of small intestine (disorder)
52457000		Ileitis (disorder)
51151007		Noninfectious ileitis (disorder)
196983007		Regional ileocolitis (disorder)
302168000		Inflammation of large intestine (disorder)
3951002		Proctitis (disorder)
313327004		Inflammatory cloacogenic polyp (disorder)
28536002		Toxic megacolon (disorder)

sTable 1.2 WHO International Statistical Classification of Diseases (ICD-10) to be used to codes to be used to identify cases of IBD and IBD subtypes

Clinical entity	ICD 10 code	Definition
Crohn's disease	K50	Any diagnostic or indicative code for Crohn's disease, excluding ulcerative colitis
Ulcerative colitis	K51	Any diagnostic or indicative code for ulcerative colitis

Appendix 2

sTable 2.1 Read and SNOMED codes to be used to identify mental health conditions

Depressive episode		
Read V2 Code	Term ID	Description

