310497006'		Severe depression (disorder)
319768000'		Recurrent major depressive disorder with melancholic features (disorder)
320751009'		Major depression, melancholic type (disorder)
321717001'		Involutional depression (disorder)
366979004'		Depressed mood (finding)
370143000'		Major depressive disorder (disorder)
394924000'		Symptoms of depression (finding)
395072006'		Counseling for postnatal depression (procedure)
430852001'		Severe major depression, single episode, with psychotic features (disorder)
450714000'		Severe major depression (disorder)
704678007'		Depressed mood with postpartum onset (finding)
712823008'		Acute depression (disorder)
718636001'		Minimal depression (disorder)
719592004'		Moderately severe major depression (disorder)
719593009'		Moderately severe depression (disorder)
720451004'		Minimal recurrent major depression (disorder)

720452006'		Moderately severe recurrent major depression (disorder)
720453001'		Moderately severe major depression single episode (disorder)
720454007'		Minimal major depression single episode (disorder)
720455008'		Minimal major depression (disorder)
723928009'		Mood disorder with depressive symptoms caused by alcohol (disorder)
723930006'		Mood disorder with mixed manic and depressive symptoms caused by alcohol (disorder)
724676000'		Mood disorder with depressive symptoms caused by sedative (disorder)
724677009'		Mood disorder with depressive symptoms caused by hypnotic (disorder)
724678004'		Mood disorder with depressive symptoms caused by anxiolytic (disorder)
724690002'		Mood disorder with depressive symptoms caused by cocaine (disorder)
724757005'		Depressive symptoms due to primary psychotic disorder (disorder)
726772006'		Major depression with psychotic features (disorder)
762321000'		Mood disorder with depressive symptoms caused by opioid (disorder)
762329003'		Mood disorder with depressive symptoms caused by stimulant (disorder)
762336002'		Mood disorder with depressive symptoms caused by hallucinogen (disorder)
762339009'		Mood disorder with depressive symptoms caused by volatile inhalant (disorder)
762512002'		Mood disorder with depressive symptoms caused by synthetic cathinone (disorder)
768835002'		Depression care management (procedure)
788120007'		Antenatal depression (disorder)
838529004'		Mood disorder with mixed depressive and manic symptoms caused by amfetamine and amfetamine derivative (disorder)
871840004'		Episode of depression (finding)

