Read CTV3 Code	Term ID	Description
SNOMED Code	Term ID	Description

sTable 2.2 Algorithms used to identify anxiety episodes, depression episodes, and recurrent major depression. Expressions in capitals equate to Boolean expressions. *More than 1 year ago. SSRIs = selective serotonin reuptake inhibitors, TCA = tricyclic antidepressants, MAOI = monoamine oxidase inhibitors, CBT = cognitive behavioural therapy.

Clinical entity	Definition
Anxiety	Any coded anxiety episode AND concurrent treatment for anxiety
Depressive episode	Any coded depressive episode AND concurrent treatment for depression
Recurrent depressive disorder	(Any historical code* for a depressive episode AND current treatment for depression) OR Any code for recurrent depressive disorder
Anxiety treatments	SSRIs, anxiolytics, counselling, CBT, and psychotherapy
Depression treatments	SSRIs, TCAs, MAOIs, counselling, CBT, and psychotherapy

sTable 2.3 WHO International Statistical Classification of Diseases (ICD-10) for mental health conditions

Clinical entity	ICD 10 code	Definition
Depressive episode	F32	Any coded depressive episode AND concurrent treatment for depression
Recurrent depressive disorder	F33	(Any historical code* for a depressive episode AND current treatment for depression) OR Any code for recurrent depressive disorder
Depression treatments	NA	SSRIs, TCAs, MAOIs, counselling, CBT, and psychotherapy
Anxiety	F41	Any coded anxiety episode AND concurrent treatment for anxiety
Anxiety treatments	NA	SSRIs, anxiolytics, counselling, CBT, and psychotherapy
Self-harm	X60-X84	Any diagnostic or indicative code for any form of self-harm, including suicide attempt
Eating disorders	F50	Any diagnostic or indicative code for eating disorders

Body image disorders	F45.2	Any diagnostic or indicative code for body image / dysmorphic disorder (excluding hypochondriacal disorders not associated with body image)
Attention-deficit disorders	F90.0	Any diagnostic or indicative code for disturbance of activity and attention
Behavioural disorders	F91 F92	Any diagnostic or indicative code for conduct disorders
Adjustment disorders	F43.2	Any diagnostic or indicative code for adjustment disorders
Acute stress disorders	F43.0	Any diagnostic or indicative code for acute stress disorders
Post-traumatic stress disorder	F43.1	Any diagnostic or indicative code for Post-traumatic stress disorder

Appendix 3

sTable 3.1 Read and SNOMED codes to be used to identify quality of life

Depressive episode		

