71336009'		Recurrent major depressive disorder with postpartum onset (disorder)
720451004'		Minimal recurrent major depression (disorder)
720452006'		Moderately severe recurrent major depression (disorder)
755331000000108'		Recurrent major depressive episodes, severe, with psychosis, psychosis in remission (disorder)
764611000000100'		Recurrent major depressive episodes, severe (disorder)
764691000000109'		Recurrent major depressive episodes, in partial remission (disorder)
764701000000109'		Recurrent major depressive episodes, in remission (disorder)

Depressive symptoms

Read V2 Code	Term ID	Description
1B17.	All	Depressed
1B1U.	All	Symptoms of depression
1BQ..	All	Loss of capacity for enjoyment
1BT..	All	Depressed mood
1BU..	All	Loss of hope for the future
2257	All	O/E - depressed
Read CTV3 Code	Term ID	Description
XE0re	All	Depressed mood
XaImU	All	Symptoms of depression
X761E	All	Loss of capacity for enjoyment

X761G	All	Loss of hope for the future
Xa3Xh	All	Feeling of hopelessness
2257.'	All	O/E - depressed
XM0CR	All	C/O - feeling depressed
X00SO	All	Depressed
XaAyM	All	Feeling hopeless
SNOMED Code	Term ID	Description
162722001'		On examination - depressed (disorder)
366979004'		Depressed mood (finding)
272022009'		Complaining of feeling depressed (finding)
307077003'		Feeling hopeless (finding)
1074741000000100'		Unable to be hopeful for future (finding)
1069851000000100'		Difficulty being hopeful for future (finding)
28669007'		Anhedonia (finding)
309838005'		Emotional upset (finding)
225014007'		Feeling empty (finding)
225457007'		Feeling suicidal (finding)
247796005'		Loss of capacity for enjoyment (finding)
430641005'		Markedly diminished pleasure (finding)
310480000'		Complaining of tearfulness (finding)
17029006'		Feeling despair (finding)
735640004'		Excessive crying of adult (finding)
271951008'		Crying associated with mood (finding)
394924000'		Symptoms of depression (finding)
Parasuicide		
Read V2 Code	Term ID	Description

U21..	All	[X]Intent self harm by hanging, strangulation/suffocation
U210..	All	[X]Int self harm by hanging, strangulation/suffocation occ home
U211..	All	[X]Intent self harm by hanging, strangulation/suffocation at res institut
U212..	All	[X]Int self harm by hanging, strangulation/suffocation in school/pub admin area
U213..	All	[X]Intent self harm by hanging, strangulation/suffocation in sport/athletic area
U214..	All	[X]Int self harm by hanging, strangulation/suffocation in street/highway

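### The Read V2, CTV3 and SNOMED lists in sTable 2.1 classify the same concepts differently, so whether a treated patient counts as a depression or anxiety event can depend on the coding system of the record

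*Combined protocol and SAP*

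**What the plan says.** The Data source section describes "pseudonymised primary care records from 700 GP practices distributed across England, Wales, Scotland and Northern Ireland" and does not state which coding system any practice or period uses. Appendix 2 then supplies "sTable 2.1 Read and SNOMED codes to be used to identify mental health conditions", with one list per system for each condition.

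The event rules are in sTable 2.2. Anxiety is "Any coded anxiety episode AND concurrent treatment for anxiety". A depressive episode is "Any coded depressive episode AND concurrent treatment for depression". Recurrent depressive disorder is met either by a depressive-episode code more than a year old with current treatment, or by a recurrent-depression code alone. Table 1 makes depression, anxiety and the composite the primary outcomes, and restricts anxiety to forms not related to phobia.

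In sTable 2.1 the SNOMED depressive-episode list includes "Depressed mood (finding". The SNOMED anxiety list includes "Separation anxiety disorder of childhood (disorder" and "Anxiety disorder of childhood OR adolescence (disorder". In sTable 3.1 the Read code for "Symptoms of depression" appears under depressive symptoms.

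No section describes a mapping between the lists, a check that they agree, an adjustment for coding system or a sensitivity analysis on it. The one Stream 1 sensitivity analysis concerns controls who do not attend their practice.

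**The concern.** For anxiety and depressive episodes the code list decides the event: a treated patient whose code is not listed does not count. The treatment requirement is the same in every system, so it cannot repair a difference between the lists. If one concept is an event in one system and not in another, the primary outcome has more than one definition inside the same analysis.

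The Stream 1 primary objective includes cumulative incidence, and the cumulative risk plots are named as key outputs. These are absolute figures. A mixture of definitions moves them even when cases and controls are perfectly balanced on coding system. In Stream 2, the mental health phenotypes at the index date form the exposure groups. There is no matching, and the adjustment set contains neither practice nor coding system.

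**Working it through.** **1. Concepts that the appendices code in more than one system.** *Episode*, *anxiety* and *adjustment* refer to the lists in sTable 2.1; *symptom* refers to the depressive-symptoms list in sTable 3.1.

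| Concept | Read V2 | CTV3 | SNOMED |
|---|---|---|---|
| Depressed mood | 1BT..: symptom only | XE0re: symptom only | 366979004: episode and symptom |
| Symptoms of depression | 1B1U.: symptom only | XaImU: symptom only | 394924000: episode and symptom |
| Complaining of feeling depressed | no matching row | XM0CR: symptom only | 272022009: episode and symptom |
| Depressed | 1B17.: symptom only | X00SO: episode (labelled depressive disorder) and symptom | not compared |
| Prolonged depressive reaction | E291.: episode and adjustment | E291.: adjustment only | 192049004: episode and adjustment |
| Brief depressive reaction | E290.: adjustment only | E290.: adjustment only | 192046006: episode and adjustment |
| Adjustment with anxious mood | E2924: adjustment only | E2924: adjustment only | 47372000: anxiety and adjustment |

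Of the codes in the depressive-symptoms list, 0 of 6 in Read V2, 1 of 9 in CTV3 and 3 of 17 in SNOMED also count as a depressive episode.

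**2. Content present in SNOMED only.** The SNOMED anxiety list holds three phobia codes (386808001, 386810004, 192611004), contrary to Table 1. It also holds symptom findings (48694002, anxiety; 162723006, anxious on examination) and procedures (313087008, counselling). Thirteen rows are childhood-type anxiety terms. One of them (192611004) is phobic, which leaves 13 − 1 = 12. Neither Read anxiety list has a phobia or childhood-specific row. The SNOMED depression list likewise includes history of depression and counselling or referral procedures.

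**3. Row counts.** Anxiety: Read V2 15, CTV3 14, SNOMED 99. Depressive episode: 50, 58 and 141. These are context only and are not evidence of non-equivalence.

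**4. Which results are exposed.** The composite includes adjustment disorder, and sTable 2.3 defines that by any relevant code without a treatment condition. The last three rows of the table therefore reach the composite in every system. The symptom-level depression codes and the phobia codes have no such cushion.

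**5. Illustration of direction.** The plan gives no figure to reproduce, and every input here is an assumption. Let r be the ratio of SNOMED to Read capture of treated episodes, and w the SNOMED share of person-time.

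- Absolute incidence relative to a Read-only definition is w·r + 1 − w. With w = 0.5 this is 1.05 at r = 1.1, 1.25 at r = 1.5 and 1.50 at r = 2.0.
- The spurious factor on the hazard ratio is (w1·r + 1 − w1)/(w0·r + 1 − w0), with w1 for cases and w0 for controls. It is 1.00 whenever w1 = w0. With w1 = 0.6 and w0 = 0.4 it is 1.06/1.04 = 1.02 at r = 1.1, 1.30/1.20 = 1.08 at r = 1.5 and 1.60/1.40 = 1.14 at r = 2.0.

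Absolute figures move with r even under balance; the hazard ratio moves only if coding system differs between cases and controls.

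**The case against.** The strongest reply is that the lists are less different than they look, and that the SNOMED list, not Read, may be the one out of line.

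- *Row counts.* A reader might infer from 99 against 15 and 14 that Read under-captures anxiety. The documents do not support that. SNOMED is more granular, and many rows split one concept, such as panic disorder by severity or anxiety by causal drug.
- *Childhood anxiety.* A reader might infer that a Read-coded child with treated separation anxiety is never an event. That is not shown. The child could carry a listed generic code (E200., Eu41z), and the documents do not show whether Read has a specific one. Nor do they support a claim that results in the youngest are distorted most.
- *Direction.* Table 1 excludes phobia-related anxiety and sTable 2.3 ties anxiety to F41. Some of the difference is therefore SNOMED over-inclusion, and simply widening Read would be the wrong repair.
- *Stream 2 outcomes.* A reader might infer that SNOMED also inflates the affective outcome through the depressed-mood codes. It does not: that outcome includes low mood, and sTable 3.1 lists the Read symptom codes for it. Only the exposure grouping is affected.
- *Mechanism.* That the difference runs along GP practices is an inference. Records might be mapped to one system first.
- *Stage.* The identification algorithm is still to be developed, and several code lists have no entries yet.

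All of these points stand as limits. They do not answer the table above, where the protocol itself holds codes for one concept in more than one system and files them differently. Granularity cannot explain that. The working status of the lists is a reason to correct them now.

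**Conclusion.** The point holds in this form: applied as written, the lists give depression and anxiety different definitions by coding system. The firmest evidence is the three symptom-level SNOMED codes, X00SO, the depressive reactions, and adjustment with anxious mood. The phobia codes are also a contradiction with Table 1. For childhood terms the conclusion is only that Read-coded cases may be missed.

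The effect falls on the absolute incidence of depression and anxiety, on the cumulative risk of the composite (partly cushioned), and on Stream 2 exposure grouping, taking sTable 2.1 as the source of those groups. The Stream 1 hazard ratio is largely protected if cases and controls share a practice, since controls also take their case's index date. However, within-practice matching is conditional on numbers.

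The size cannot be computed from the documents. The conclusion assumes that records in more than one system enter the analysis without prior mapping. Supplying three lists suggests this, but the protocol does not say so.

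**What to change.** Before extraction, define each outcome once as a list of clinical concepts and map it to all three systems. Specifically:

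- Remove 366979004, 394924000 and 272022009 from the SNOMED depressive-episode list; they remain under depressive symptoms.
- Decide one classification, applied in every system, for the concept behind X00SO, for prolonged and brief depressive reaction (E291./192049004 and E290./192046006), and for adjustment with anxious mood (E2924/47372000).
- Remove 386808001, 386810004 and 192611004 from the SNOMED anxiety list, to agree with Table 1.
- Treat symptom, history and procedure codes alike across systems, and include childhood anxiety terms in Read where such codes exist.
- State which systems are present by practice and period, and whether records are mapped before analysis.
- Rerun the primary analysis on concepts present in all three systems as a sensitivity check.

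The cost is code-list editing, a slightly lower SNOMED event count and one additional run.
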